## 2.6 Change from Statistical Section of the Protocol

As per section 9.4.1 of the protocol it stated that all analyses will be performed by parent study (PVO-1A-301 or PVO-1A-202/PVO-1A-204), by palovarotene status at the time of transition to Study CLIN-60120-452 (treated, not treated) and treatment regimen (chronic treatment only, flare-up treatment only, chronic & flare-up treatment) and overall.

However, all analyses will only be performed overall and by treatment regimen (chronic treatment only, flare-up treatment only, chronic & flare-up treatment).

## 3 PLANNED ANALYSES

### 3.1 Data Monitoring

Participant safety will be regularly monitored by an external Independent Data Monitoring Committee (IDMC), which includes safety signal detection at any time during the study. Three IDMC meetings are planned to take place over the maximum three-year duration of the study. Details related to IDMC membership, responsibilities, procedures and roles are described in the IDMC charter and the statistical analysis is described in the IDMC SAP.

### 3.2 Interim Analysis

No formal interim analysis will be performed. A stand-alone final report for the qualitative participant interviews will be made available once enrolment and all interviews have been completed within 1 year following the Inclusion Visit.

### 3.3 Final Analysis

The final analysis will be completed after database lock when all participants have completed the study.

## 4 ANALYSIS SETS

For the purposes of analysis, the following analysis sets are defined:

Participant Analysis Set	Description
Screened Set	All participants who signed the ICF
Enrolled Set	The Enrolled Set will contain all participants who were assigned to receive palovarotene in Study CLIN-60120-452. Participants will be included based upon the "Is participant included in the study?" question within the eCRF.
Full Analysis Set (FAS)/Safety Analysis Set (SAS)	The FAS/SAS will contain all participants who received at least one dose of palovarotene during Study CLIN-60120-452.
Per Protocol (PP) Set	The PP set will contain all participants from the FAS who did not experience any major protocol deviations that may interfere with safety/efficacy evaluations. Please refer to section 5.3 for details regarding the management of deviations.

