Unit Dose Strength(s)	Each capsule contains 1 mg, 1.5 mg, 2.5 mg, 5 mg or 10 mg of palovarotene as active ingredient
Dosage Level(s)	
Chronic/flare-up regimen:
 
Chronic treatment 5 mg once daily (or at the dose received during participation in the parent study at the time of transition to Study CLIN-60120-452, or prior to interrupting/stopping palovarotene treatment)
 
Flare-up treatment 20 mg once daily for 4 weeks (28 days) 10 mg once daily for 8 weeks (56 days) Persistent flare-up symptoms: extension of 10 mg once daily in 4-week increments Intercurrent flare-ups (new flare-up location or marked worsening of original flare-up): 12-week flare-up treatment should be restarted
 
Chronic treatment: once daily, 5 mg or at the dose received during participation in the parent study at the time of transition to Study CLIN-60120-452 or prior to interrupting/stopping palovarotene treatment.
 
Flare-up treatment: increase in dose at the time of a flare-up (or substantial high risk traumatic event likely to lead to a flare-up) to 20 mg once daily for 4 weeks (28 days), followed by 10 mg once daily for 8 weeks (56 days) for a total of 12 weeks (84 days) (20/10 mg flare-up treatment) even if symptoms resolve earlier.
 
Flare-up treatment should begin at the onset of the first symptom indicative of a FOP flare-up or substantial high-risk traumatic event likely to lead to a flare-up. Symptoms of a FOP flare-up typically include but are not limited to localised pain, soft tissue swelling/inflammation, redness, warmth, decreased joint range of motion, and stiffness. Chronic treatment should cease at the time of initiation of flare-up treatment, re-initiation of the chronic daily treatment should occur after completion of the flare-up treatment.
 
Flare-ups can occur in the absence of any apparent causative factor, but there is a high risk that substantial traumatic events (e.g. surgery, intramuscular immunisation, mandibular blocks for dental work, muscle fatigue, blunt muscle trauma from bumps, bruises, falls or influenza-like viral illnesses), can lead to a flare-up and result in heterotopic bone formation. Flare-up treatment should be initiated at the time of such events.
 
Persistent flare-up symptoms: treatment may be extended in 4-week intervals with 10 mg palovarotene and continued until the flare-up symptoms resolve.
 
Intercurrent flare-up: if the participant experiences an intercurrent flare-up (new flare-up location or marked worsening of the original flare-up) at any time during the flare-up treatment, then the 12-week flare-up treatment should be restarted.
 
In the case of any intolerable adverse reactions, the daily dose of the chronic/flare-up regimen can be reduced (see Section 6.5).
 
Flare-up only regimen: If the participant experiences intolerable adverse reactions while taking chronic daily treatment and dose reduction does not alleviate the adverse reactions, then the participant may take palovarotene only at the time of flare-up (or substantial high-risk traumatic event).

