9.4 Statistical Analyses

9.4.1 *General Considerations*

Statistical evaluation will be performed using Statistical Analysis System (SAS[®]) (Version 9.4 or higher).

No formal statistical testing will be performed. All the analyses will be primarily descriptive in nature. If p-values are presented, they will be for exploratory purposes only.

For descriptive analyses, summary statistics will be presented at each scheduled visit and will include sample size, number of available observations (N), number of missing observations (missing), mean, 95% CIs of the mean/median, standard deviation (SD), number of nonmissing observations (n), median and range for continuous variables and scores. For categorical or discrete variables, the absolute and relative (percentage) numbers based on the nonmissing number of observations for each category will be presented, including 95% CIs.

Missing data will not be replaced but will be displayed in all relevant tables.

The Inclusion Visit is the first study visit (Day 1) and first administration of palovarotene in Study CLIN-60120-452 (and corresponds to the EOS Visit of the parent study for assessments already performed in the parent study).

All analyses will be performed by parent study (PVO-1A-301 or PVO-1A-202/PVO-1A-204), by palovarotene status at the time of transition to Study CLIN-60120-452 (treated, not treated) and treatment regimen (chronic treatment only, flare-up treatment only, chronic & flare-up treatment) and overall.

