##### Treatment Regimen

- Chronic Treatment Only
- Flare-up Treatment Only
- Chronic and Flare-up Treatment
- Not Treated (Only required on outputs not using FAS/SAS)

The treatment regimen will be derived from the dosing form collected in CLIN-60120-452 study. All dosing records will be used. Cases where the treatment regimen is not available from the CRF will be discussed with the IPSEN team on a case-by-case basis.

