### 5.1.3 *Baseline value*

Unless otherwise specified, baseline is defined as the last non-missing measurement taken prior on the day of first Investigational Medicinal Product (IMP) administration in study CLIN-60120-452. This includes data collected at the Inclusion Visit and data transferred from the final parent study databases (either programmatically or entered by site). See the schedule of assessments in section 2.5 for the method of collection of data for the Inclusion Visit.

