### 5.1.4 *Reference Start Date and Study Day*

Reference start date is defined as the day of the first IMP administration of palovarotene (Day 1) in Study CLIN-60120-452. Study day will be calculated as:

- The difference between the event date and the reference date plus one day, if the event is on or after the reference date.
- The difference between the event date and the reference date, if the date of event is prior to the reference date.

Study day will appear in any listings where an assessment date or event date appears.

In case of partial or missing event date, study day will appear missing while any associated durations will be presented based on the imputations described in appendix A3.

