## 5.7 Primary and Secondary Analysis

### 5.7.1 General Considerations

The FAS/SAS will be used for the analysis of the primary and secondary endpoints. Analyses of the secondary endpoints will be repeated on the Per Protocol (PP) Set if ≥10% of participants are excluded from the FAS/SAS Set.

All analyses will be performed overall and by treatment regimen (chronic treatment only, flare-up treatment only, chronic and flare-up treatment).

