## **6 DATA HANDLING**

### **6.1 Visit window**

The below time windows for visit/timepoints will be used for analyses:

Analysis Visit	Scheduled Day	Visit Window
Baseline	Up to Day 1	≤ Day 1 Last non-missing measurement taken prior to first Investigational Medicinal Product (IMP) administration in study CLIN-60120-452
Month 6	182	Day 2-274
Month 12	365	Day 275-456
Month 18	547	Day 457-639
Month 24	730	Day 640-821
Month 30	912	Day 822-1003
Month 36	1095	≥ Day 1004

For post-baseline visit windows, the following applies when there are multiple assessments in a particular visit window, the closest to the scheduled day is chosen (if two assessments have the same distance, then the later one will be chosen).

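### Baseline, study day and visit windows start at the first in-study dose instead of the Inclusion Visit, which mislabels visits for any participant first dosed about 92 days or more after Inclusion

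*SAP*

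**What the plan says.** The SAP ties its time scale to dosing. Section 5.1.4 states: "Reference start date is defined as the day of the first IMP administration of palovarotene (Day 1) in Study CLIN-60120-452". Section 5.1.3 says that, unless otherwise specified, "baseline is defined as the last non-missing measurement taken prior on the day of first Investigational Medicinal Product (IMP) administration". The Baseline row of the window table in Section 6.1 reads: "Last non-missing measurement taken prior to first Investigational Medicinal Product (IMP) administration in study CLIN-60120-452". The post-baseline windows are Day 2-274 for Month 6, 275-456 for Month 12, 457-639 for Month 18, and so on. Where two assessments share a window, the one nearer the scheduled day is used. Flare-ups (5.7.3.7) and extra bone growths (5.7.3.8) are assigned to the same windows by start date.

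Membership of the analysis set also depends on dosing. SAP 4 gives the one-dose rule, as protocol 9.3 does: "The FAS/SAS will contain all participants who received at least one dose of palovarotene during Study CLIN-60120-452". SAP 5.7.1 adds: "The FAS/SAS will be used for the analysis of the primary and secondary endpoints". The Per Protocol Set is a subset of that set.

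The protocol takes the two anchors to be the same day. Section 9.4.1 says: "The Inclusion Visit is the first study visit (Day 1) and first administration of palovarotene in Study CLIN-60120-452". The secondary change endpoints in protocol Section 3 and SAP 2.1 are defined from the Inclusion Visit.

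Protocol 6.1 also describes a flare-up-only regimen, for use when dose reduction does not relieve intolerable reactions on chronic treatment: "then the participant may take palovarotene only at the time of flare-up (or substantial high-risk traumatic event". The same section bases each participant's treatment on the regimen and dose carried over from the parent study.

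**The concern.** The protocol's equation of Inclusion with first dose fails for a participant who enters with no dose due until a flare-up or high-risk traumatic event. If that event comes late, the SAP's clock starts late. Earlier follow-up visits then count as baseline or carry too low a month label, and the flare-up that started the clock is classed as pre-treatment history. If no event comes, the participant is absent from every FAS/SAS table. Being analysed would then depend partly on having had a flare-up, which is itself a secondary endpoint.

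The conflict also sits inside the SAP. The secondary sections ask for change from the inclusion visit, but the list of analysis visits in 5.1.1.3 has Baseline and no Inclusion entry. Where the two dates differ, the programmer has to choose.

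**Working it through.** The plan states no figure to reproduce: the study is descriptive and 87 is a cap on enrolment. The check applies the SAP's own rules to late first doses.

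**Visit labels.** Count days with Inclusion as day 1. Let *v* be the visit day (scheduled days 182, 365, 547 and so on, from SAP 6.1) and *f* the day of first dose. By SAP 5.1.4, study day is *v* − *f* + 1 if *v* ≥ *f*, and *v* − *f* otherwise.

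| First dose on day | Inclusion | 6-month visit | 12-month visit | 18-month visit |
|---|---|---|---|---|
| 1 | Baseline | 182, Month 6 | 365, Month 12 | 547, Month 18 |
| 30 | Baseline | 153, Month 6 | 336, Month 12 | 518, Month 18 |
| 100 | Baseline | 83, Month 6 | 266, Month 6 | 448, Month 12 |
| 200 | Baseline | −18, Baseline | 166, Month 6 | 348, Month 12 |
| 400 | Baseline | −218, Baseline | −35, Baseline | 148, Month 6 |

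- The 12-month visit enters the Month 6 window when 365 − *f* + 1 ≤ 274, that is *f* ≥ 92.
- At *f* = 100, two visits share the Month 6 window. Their distances from day 182 are 182 − 83 = 99 and 266 − 182 = 84. The 12-month value is therefore tabulated as Month 6, and the true 6-month value drops out of the tables.
- The 6-month visit reaches Day 1 or earlier when 182 − *f* + 1 ≤ 1, that is *f* ≥ 182. It can then become the baseline.
- With first dose on day 1 or day 30, no label changes.

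These thresholds assume visits on their scheduled days; the ±1 month allowance moves them for individuals.

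**Flare-up counts.** A flare-up that prompts the first dose starts on or before the dose, so on or before Day 1. It falls in the Baseline window and outside the by-visit post-inclusion counts.

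**Flare-up rates.** The individual and global rates in SAP 5.7.3.7 use time from informed consent, so the clock does not affect them. Only the population does.

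**Never-dosed participants.** The documents give neither the number of flare-up-only entrants nor a flare-up rate. Assume Poisson flare-ups at *r* = 0.5, 1 or 2 per year, *T* = 2 years of follow-up, and no dosing for trauma.

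- Probability of no flare-up, P0 = exp(−*rT*): 0.368, 0.135, 0.018.
- Rate among the flare-up-only entrants who are kept, relative to the true rate, 1/(1 − P0): 1.58, 1.16, 1.02.
- Overall rate with *k* such entrants of 87, relative to the true rate, 87/(87 − *k*·P0). Smallest case, *k* = 1 and *r* = 2: 87/(87 − 0.018) = 1.0002. Largest, *k* = 10 and *r* = 0.5: 87/(87 − 3.68) = 1.044.

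**Delay among those dosed.** Only waits that end within follow-up create a Day 1, so the mean wait is 1/*r* − *T*·exp(−*rT*)/(1 − exp(−*rT*)).

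- *r* = 2, *T* = 1: 0.5 − 0.135/0.865 = 0.34 years, about 4.1 months.
- *r* = 0.5, *T* = 3: 2 − 3 × 0.223/0.777 = 1.14 years, about 13.7 months.

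Both means exceed 92 days.

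**The case against.** The strongest objection is that the affected group may be empty. Protocol 4.1 has enrolled participants dosed once daily, and 6.1 places treatment initiation at the Inclusion Visit. Flare-up-only is described as a switch made while on chronic treatment. Anyone who switches in-study already has a dose and a Day 1 at or near Inclusion, and so does anyone who transitions during flare-up treatment. Protocol Table 2 also says that participants intolerant to prior palovarotene are not included. Most of this stands and limits the point to entrants with no dose at Inclusion. It does not settle the matter. The carry-over wording leaves such entry open, and the exclusion list in 5.2 that Table 2 cites names unresponsiveness, not intolerance. Those two passages need reconciling.

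A reader might take the SAP's group label "Not Treated (Only required on outputs not using FAS/SAS" as proof that flare-free entrants are expected. It is not: listings use the Screened Set and are sorted by regimen, so screen failures need that label. Nor does the planned flare-up-only column prove it. That column is derived from in-study dosing records, so it could hold someone who transitioned mid-flare-up and left before chronic dosing resumed.

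It can also be said that 5.1.3 yields wherever another section specifies otherwise, and the sections on FOP-PFQ, PROMIS, CAJIS, assistive devices and lung function do specify the inclusion visit. That protects the reference value but not the label. With first dose on day 400, the Month 6 row would hold an 18-month change.

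Finally, the one-dose FAS is the protocol's own choice (9.3 and 9.4.3), and most of the efficacy objectives are framed as under palovarotene treatment. This stands, and it argues against replacing the FAS as the main set.

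**Conclusion.** The concern holds for a limited group. The SAP's dose-based clock conflicts with protocol 9.4.1 and with endpoints defined from the Inclusion Visit. The conflict matters only for participants whose first in-study dose comes well after Inclusion, a group of unstated and possibly zero size. For them, a first dose from about day 92 shifts visit labels, one from about day 182 turns a follow-up visit into the baseline, and the triggering flare-up leaves the by-visit counts. A participant never dosed is missing from all FAS/SAS summaries, though still present in the listings and in the Enrolled Set tables.

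The documents do not support the broader inference that flare-up-only participants in general lose their flare-free members from the efficacy analyses: in-study switchers and those transitioning on flare-up treatment are unaffected. Under the assumed inputs, the distortion of the overall flare-up rate is 0.02% to 4.4%. Within the affected entrants it is larger (a factor of 1.02 to 1.58 over 2 years), and dosing for trauma would reduce it.

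One uncertainty remains. SAP 5.8.2.1 takes the first dose date from the first Dosing Form record, and 5.7.2.2 recognises 0 mg records, so it is unclear how Day 1 would be coded for such an entrant.

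**What to change.** In SAP 5.1.3, 5.1.4 and 6.1, set Day 1, baseline and visit windows to the Inclusion Visit for by-visit efficacy summaries and for assigning flare-ups and extra bone growths to windows. Baseline would be the last non-missing value at or before that visit, including values taken over from the parent study. Keep first in-study dose as the anchor for TEAEs and exposure, and say that a 0 mg record is not a dose.

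Keep the protocol-defined FAS as the main set. SAP 5.2 already tabulates participants enrolled and treated; add an explicit count of those enrolled but never dosed. If it is not zero, add a supportive summary of flare-ups and the other secondary endpoints on all enrolled participants with an Inclusion Visit. Record both changes in SAP 2.6.

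The cost is SAP wording before database lock and, at most, one supportive table with a slightly different N. Nothing changes for a participant dosed on the day of Inclusion.

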## 5 STATISTICAL METHODS/ANALYSES

The statistical analyses will be performed in accordance with ICH E9 guidelines.

### 5.1 General Considerations

No formal statistical testing will be performed. All the analyses will be primarily descriptive in nature. If p-values are presented, they will be for exploratory purposes only. Confidence intervals will be 95%, unless otherwise specified in the description of the analyses.

With the exception of the QoL questionnaires, where missing data will be handled based upon the calculation of the derived scores, missing data will not be replaced but will be displayed in all relevant tables.

All analyses will be performed overall and by treatment regimen (chronic treatment only, flare-up treatment only, chronic & flare-up treatment).

All listings will be presented on the screened set.

All statistical analyses will be performed using the Statistical Analysis System® software version 9.4.

### **5.1.1 Outputs Presentation**

#### *5.1.1.1 Tables Header*

All summary tables will be presented overall and by treatment regimen.

#### *5.1.1.2 Presentation of Groups*

Tables, Figures and Listings (TFLs) will be displayed using the following group labels, in the order presented:

##### Overall

- Overall

Overall includes all participants.

##### Treatment Regimen

- Chronic Treatment Only
- Flare-up Treatment Only
- Chronic and Flare-up Treatment
- Not Treated (Only required on outputs not using FAS/SAS)

The treatment regimen will be derived from the dosing form collected in CLIN-60120-452 study. All dosing records will be used. Cases where the treatment regimen is not available from the CRF will be discussed with the IPSEN team on a case-by-case basis.

